
Schedule of Events Zone 0/1 Cohorts
	
Screening Evaluation: (Within 30 days prior to enrollment unless otherwise noted)
 
 • Physical examination, medical history • Modified Rankin Scale • Spinal Cord Ischemia Scale • NIH Stroke Scale • Serum creatinine concentration • Spiral Computed Tomographic Angiography (CTA) of the chest, abdomen, and pelvis (contrast only) within 90 days prior to the Phase 2 procedure • Radiological Evaluation of the Head/Neck within 90 days prior to Phase 1 procedure 
Phase 1 Evaluation at least 24 hours but no more than 60 days following the completion of the revascularization procedure:
 
 • Physical examination • Modified Rankin Scale

- Spinal Cord Ischemia Scale
- In addition, NIH Stroke Scale should be performed for any Subject suspected of having a stroke event that undergoes the treating site's stroke Protocol during the study interval from the initiation of surgical revascularization procedure until discharge post-index endovascular procedure, and it should be performed as soon as possible after learning of the event

Phase 2 Procedure at least 24 hours but no more than 60 days following the completion of the revascularization procedure:

- Endovascular repair with the TBE Device
- Post deployment angiogram

Post Procedure:

(Performed prior to discharge unless otherwise noted)

- Physical examination
- Modified Rankin Scale
- Spinal Cord Ischemia Scale
- NIH Stroke Scale
- In addition, NIH Stroke Scale should be performed for any Subject suspected of having a stroke event that undergoes the treating site's stroke Protocol during the study interval from the initiation of surgical revascularization procedure until discharge post-index endovascular procedure, and it should be performed as soon as possible after learning of the event

Follow-Up Evaluations:

Intervals: 1, 6, 12, 24, 36, 48, and 60 months post-treatment

- Physical examination
- Modified Rankin Scale (also completed at 3 months for Subjects suspected of experiencing a stroke event through 30 days)
- Spinal Cord Ischemia Scale
- NIH Stroke Scale (one month only)
- Spiral CTA of the chest (contrast)
- Dissection Subjects only: Spiral CTA of the chest, abdomen and pelvis (contrast)
- Spiral CT of the chest (non-contrast – one month only, or if endoleak suspected)

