2.3.1.1 Zone 2 Aneurysm Cohort

The Primary Endpoint for the Zone 2 aneurysm cohort will be a composite of the following events through 12 months (through day 546 unless otherwise specified in study protocol component definitions) following the index endovascular procedure:

- Device Technical Success
- Absence of the following:
 - Aortic rupture;
 - Lesion-related mortality;
 - Disabling stroke
 - Permanent paraplegia
 - Permanent paraparesis
 - New onset renal failure requiring permanent dialysis
 - Additional unanticipated post-procedural surgical or interventional procedure related to the device, procedure, or withdrawal of the delivery system.
- 2.3.1.2 Zone 0/1 Aneurysm Cohort

[figure not shown]
The Primary Endpoint for the Zone 0/1 aneurysm cohort will be Strategy Success.

Strategy Success (For planned staged procedures – landing zone optimization, transposition, and device placement – through one month following last planned procedure) and is defined as follows: a composite of the following events from the time of enrollment through one month following the index endovascular procedure (through day 59 unless otherwise specified in study protocol component definitions):

[figure not shown]
- Initiation of the index endovascular procedure following the debranching procedure
- Device technical success for the index endovascular procedure
- Absence of the following :
 - Aortic rupture
 - Lesion-related mortality
 - o Disabling Stroke
 - Permanent paraplegia
 - Permanent paraparesis
 - New onset renal failure requiring permanent dialysis

GORE CONFIDENTIAL INFORMATION

 Additional unanticipated post-procedural surgical or interventional procedure related to the device, procedure, or withdrawal of the delivery system.

GORE CONFIDENTIAL INFORMATION

2.4 **Statistical Hypotheses**

- 2.4.1 Performance Goal Derivation
 - 2.4.1.1 Zone 2 Aneurysm Cohort

Historical TAG/CTAG results (TAG 99-01, TAG 03-03, TAG 04-02, TAG 05-02, TAG 08-03) were re-analyzed to determine the Zone 2 aneurysm cohort performance goal for the Primary Endpoint (see study protocol for this data). Subjects treated for DTA aneurysms with proximal device placement in Zone 2

GORE CONFIDENTIAL INFORMATION

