^d CTA of chest/abdomen/pelvis at Screening. CTA of chest at all follow-up visits, except for Dissection Subjects who must have a CTA of chest/abdomen/pelvis at all visits. Imaging Guidelines for CT are located in Protocol. MRA may be used in place of CTA during follow-up if the Subject is contraindicated for CTA.

^e Screening CTA must be ≤ 90 days prior to enrollment

^f NIH Stroke Scale should be performed for all subjects during Screening, Discharge and 1 Month visits. NIHSS should also be performed for any Subject suspected of having a stroke event that undergoes the treating site's stroke Protocol during the study interval from the initiation of the index endovascular procedure until discharge. The scale should be performed as soon as possible after learning of the suspected event.

		Tr	reatm	ent					24
	Screening	Phase 1 Procedure	Phase 1 Evaluation	Phase 2 Procedure	Discharge	1 month	6 months	12 months	24, 36, 48, and 60 months
Informed Consent	х								
Demographics and Medical History	х								
Physical Examination	х		X۵		х	х	х	х	х
Modified Rankin Scale ^c	х		x		х	Xď	х	x	х
Spinal Cord Ischemia Scale ^c	х		x		х	х	х	x	х
Brachial and Ankle Pressures (Optional)	х		x		X e	х	х	х	х
Serum Creatinine Concentration	х								
Spiral CTA (contrast) ^f	Xg					х	х	x	х
Spiral CT (non-contrast) ^f						х			
Angiogram at Completion of Procedure				x					
CTA of the Head/Neck h	х								
NYHA Score, ASA Score	х								
ISS Score, Glasgow Coma Score (Traumatic Transection Subjects only)	x								
NIH Stroke Scale (NIHSS) ⁱ	х				x	x			

Table 2: Zone 0/1 Subject Evaluations and Post-Treatment Follow-up Schedule

^a Phase 1 Evaluation should be performed at least 24 hours after the revascularization procedure but within 30 days post treatment ^b Subjects who are withdrawn prior to the Phase 2 Procedure should also have a Physical Exam at one month post Phase 1 procedure

^c If subject is unable to return to the site for a follow-up visit, they may be contacted by telephone to evaluate the Modified Rankin Scale and Spinal Cord Ischemia Scale

^d For subjects suspected of having a stroke event within 30 days following the index endovascular procedure an additional MRS score should be completed at 90 days following the suspected stroke event but no greater than 120 days post index endovascular procedure.

^eWithin 48 hours of index endovascular procedure

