5.1.1.2 Zone 0/1 Aneurysm Cohort

The composite Primary Endpoint analysis population (to test the hypothesis) for the Zone 0/1 aneurysm cohort will be among enrolled Subjects (excluding those with a CEC adjudicated 'major' inclusion/exclusion criteria violation or FDA mandated exclusion) and is outlined as follows based on events as described in Section 2.3.1.2:

- Subjects with an event any time \leq 59 days are a failure regardless of whether they had imaging in one month window
- Subjects that don't have imaging in the one month window and don't have an event \leq 59 days are excluded
- Subjects with imaging in one month window and no event reported \leq 59 days are successes
- Subjects with >1 event just count once as failures

The analysis population for the Zone 0/1 Aneurysm cohort will also exclude any Subjects treated with a 49/53mm device since those device sizes have been removed from this study. Any Subjects enrolled and treated with those device sizes will not be counted in the N=50 enrollment and replacement Subjects will be enrolled to keep N=50. The 49/53mm Subjects will be summarized separately and followed per the Protocol.

This analysis will also be repeated with 12 month results (following the same analysis population logic as that outlined for the Zone 2 aneurysm cohort in Section 5.1.1.1) with the exception that no hypothesis will be tested.

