8.1 Analysis Tables

Appendix A: Adjudication of Primary Endpoints and Success Outcomes

[figure not shown]
The table below describes the responsible party for the determination and adjudication of each specific Primary Endpoint and The time periods for these endpoint/outcome determinations are described in Section 2.3. In addition, the third column explains what CRF, question (using permanent internal database short label), and question response will be used to determine endpoint/outcome failure.

[figure not shown]
Key Outcome	Endpoint/Outcome Determination	Case Report Form, Question Short Label (Response Option Picked to Determine Endpoint / Outcome Failure)
Device Technical Success for index endovascular procedure	Composite Event - Not Applicable	
Successful access and delivery	Site Investigator	TX2, Question 'TX2 Access' (No)
Patency of the graft	Site Investigator	 TX2, Question 'TX2 Patent' (No)
Unanticipated additional procedure related to the device, procedure, or withdrawal of the delivery system	Site Investigator	 TX2, Question 'TX2 Unanticipated' (Yes)
Aortic Rupture	Site Reported AE followed by CEC Adjudication Or Core Lab	 Event reported in AE form and CEC Adjudicated Question 'CEC Aortic Rupture' (Yes) or POSTCL-ANU, Question 'Post Lesion Rupture' (Yes – Within area of treatment) or POSTCL-DIS, Question 'Post Dis Rupture' (Yes – Within area of treatment) or Event reported in AE form and OMA Question 'OMA1 Aortic Rupture' (Yes)
Lesion-related Mortality	Site Reported AE followed by CEC Adjudication	 Death reported (AE, Question 'AE Outcome' (Death)) and CEC Adjudicated Question 'CEC Lesion Related Mortality 2' (Yes) or Death reported (AE, Question 'AE Outcome' (Death)) and OMA Question 'OMA1 Lesion Related Mortality 2' (Yes)
Disabling Stroke	Site Reported AE followed by CEC	Event reported in AE form and CEC8 or CEC9

GORE CONFIDENTIAL INFORMATION

Key Outcome	Endpoint/Outcome Determination	Case Report Form, Question Short Label (Response Option Picked to Determine Endpoint / Outcome Failure)
	Neurologist Review and adjudication	Question 'CEC Disabling' (Yes)
Permanent Paraplegia	Site Reported AE followed by CEC Adjudication	Event reported in AE form and CEC Adjudicated Question 'CEC Paraplegia' (Yes)
Permanent Paraparesis	Site Reported AE followed by CEC Adjudication	 Event reported in AE form and CEC Adjudicated Question 'CEC Paraparesis' (Yes)

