Additional unanticipated post- procedural surgical or interventional procedure related to the device, procedure, or withdrawal of the delivery system	Site Reported AE with an unanticipated post- procedural surgical or interventional procedure followed by AE adjudication by CEC.	 Event reported in AE form where Site answers Question 'AE SAE Unanticipated' (Yes) and CEC Adjudicated Question 'CEC Reintervention' (Yes) or Event reported in AE form where Site answers Question 'AE SAE Unanticipated' (Yes) and OMA Question 'OMA1 Reintervention' (Yes)
Initiation of the index endovascular procedure following the debranching procedure (Zone 0/1 cohorts only)	Site Reported Treatment Data	PFU, Question 'PFU Continue' (No)

Key Outcome	Endpoint/Outcome Determination	Case Report Form, Question Short Label (Response Option Picked to Determine Endpoint / Outcome Failure)

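### Zone 0/1: a subject who never starts Phase 2 is a failure by definition, but could be excluded under the field mapping visible in Appendix A

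*SAP*

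**What the plan says.** **Definition.** SAP Section 2.3.1.2 sets the Zone 0/1 primary endpoint, Strategy Success, as "a composite of the following events from the time of enrollment through one month following the index endovascular procedure". The first condition is "Initiation of the index endovascular procedure following the debranching procedure". The Protocol summary lists the same condition.

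**Mapping.** SAP Appendix A introduces its third column as the form, question and answer of which the "question response will be used to determine endpoint/outcome failure". For this component the visible entry is "PFU, Question 'PFU Continue' (No", closed by a bracket. The determination column gives the source as treatment data reported by the site. Section 5.3.1 calculates composite success from the Appendix A details.

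**Population.** SAP Section 5.1.1.2 classifies subjects by the events of Section 2.3.1.2. A subject with an event by day 59 is a failure. The next rule, "Subjects that don't have imaging in the one month window and don't have an event" by day 59, leads to exclusion. Table 4 sets the one-month analysis window at days 15 to 59, with Phase 2 as day 0.

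**Subjects who stop between phases.** The SAP foresees them. Table 2, footnote b, says: "Subjects who are withdrawn prior to the Phase 2 Procedure should also have a Physical Exam at one month post Phase 1 procedure". The footnote names no imaging. The Protocol's Zone 0/1 schedule has the "Phase 2 Procedure at least 24 hours but no more than 60 days following the completion of the revascularization procedure".

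**The concern.** The endpoint asks whether the index procedure was started. The visible mapping asks for one form answer and lists no check against a procedure record, although Section 4.1 lists initial endovascular procedure data among those collected.

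The Phase 1 Evaluation can take place 24 hours after debranching and Phase 2 as late as 60 days after it. A subject could be recorded as continuing and then withdraw, or die of a cause not judged lesion-related, before Phase 2. A subject with no PFU answer is in the same position.

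Failing to complete the planned strategy is what this component is there to capture. If such subjects leave the denominator, the success rate can only rise. The Zone 0/1 sample size makes no allowance for attrition, and the test on about 50 subjects is sensitive to one or two reclassifications.

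**Working it through.** **Step 1. Follow one subject through the rules.** The subject has Phase 1, is marked to continue or has no PFU answer, never starts Phase 2, and has no rupture, lesion-related death, disabling stroke or other listed event.

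- Non-initiation in Appendix A: 'PFU Continue' is not No, so no failure is mapped.
- Device Technical Success in Appendix A: read from the TX2 form for the index procedure, and each item needs an explicit Yes or No to fail. Without that procedure, no such answer is expected.
- One-month imaging: days 15 to 59 count from Phase 2, so the window does not exist.
- Section 5.1.1.2 read with Appendix A: no event and no imaging, so excluded.
- Section 5.1.1.2 read with Section 2.3.1.2: a condition of success is not met, so a failure.

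The two readings classify the same subject differently.

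**Step 2. Reproduce the plan's threshold.** Inputs: n = 50 and goal 60% (SAP text on the Zone 0/1 hypothesis and sample size); one-sided exact test at alpha 0.05 (Section 5.3.1). The lower bound L for x successes of n solves P(X ≥ x | n, L) = 0.05, that is, the 5% quantile of Beta(x, n − x + 1).

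- 37/50 = 74.0%: P(X ≥ 37 | 50, 0.60) = 0.0280, L = 61.9%, goal met.
- 36/50 = 72.0%: P(X ≥ 36 | 50, 0.60) = 0.0540, L = 59.7%, goal not met.

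The plan's 74% is reproduced as the smallest passing result (at least 74%).

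**Step 3. Effect at the boundary.** Assume that k of 50 subjects are in the gap; the documents give no k. For each k, take the smallest passing count after exclusion and put the same successes over 50.

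| k | Excluded | L | Goal | Counted as failures | L | Goal |
|---|---|---|---|---|---|---|
| 1 | 36/49 (73.5%) | 61.2% | met | 36/50 (72%) | 59.7% | not met |
| 2 | 35/48 (72.9%) | 60.4% | met | 35/50 (70%) | 57.6% | not met |
| 3 | 35/47 (74.5%) | 61.9% | met | 35/50 (70%) | 57.6% | not met |
| 4 | 34/46 (73.9%) | 61.2% | met | 34/50 (68%) | 55.5% | not met |
| 5 | 33/45 (73.3%) | 60.4% | met | 33/50 (66%) | 53.5% | not met |

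**Step 4. Effect on type I error.** Let true success among all enrolled be 60%, and let each subject fall in the gap with probability q (assumed). The number excluded is k ~ Bin(50, q). The remaining subjects succeed with probability 0.60/(1 − q) and are tested at the exact critical count c for 50 − k:

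P(goal met) = Σₖ P(k) × P(X ≥ c(50 − k) | 50 − k, 0.60/(1 − q)).

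| q | Expected number of 50 | 0.60/(1 − q) | P(goal met) if excluded |
|---|---|---|---|
| 0% | 0 | 0.600 | 2.8% |
| 2% | 1 | 0.612 | 4.9% |
| 4% | 2 | 0.625 | 7.3% |
| 6% | 3 | 0.638 | 10.2% |
| 10% | 5 | 0.667 | 18.7% |

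If these subjects count as failures, the figure is 2.8% at every q.

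**The case against.** A reader might infer that the SAP directs the exclusion of every subject who fails to reach Phase 2, on the strength of a site's statement of intent. The documents do not support that, for four reasons.

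- Section 5.1.1.2 cites Section 2.3.1.2, under which non-initiation is itself a failure. On that wording the imaging rule is never reached. This stands, and it makes the point an inconsistency between definition and mapping. It does not settle the matter for the sponsor, because Section 5.3.1 sends the calculation to Appendix A.
- 'PFU Continue' is an internal short label. The wording of the question, when it is answered, and whether it must be updated if Phase 2 is cancelled are not shown. The source description fits a record of what happened as well as it fits a forecast. This stands, and the point is conditional on it.
- The public Appendix A text is incomplete; for example, it shows no row for renal failure. A further trigger for non-initiation may exist in text that is not visible.
- A subject with any other listed event after enrollment still fails. The affected group is therefore narrow, and Table 4's ideal interval between phases is only 1 to 7 days.

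On size, the comparison of 36/50 with 36/49 sits at the critical count, where any single reclassification matters, and at an assumed 2% the type I error is still within 5%. Both remarks are fair. Section 5.3.1 also refers to missing-data sensitivity analyses in Section 5.5.1. Their text is not available, and they would not change how the primary analysis classifies the subject.

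**Conclusion.** The point holds as a conditional inconsistency. The definition makes a non-starter a failure. The mapping visible in Appendix A, combined with the imaging rule, would exclude a non-starter who was marked to continue or has no PFU answer and who has no other listed event. The conclusion assumes that the PFU answer is not updated when Phase 2 does not take place, and that no further trigger lies in text not shown.

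The direction of the bias is certain: exclusion can only favour the device. Its size depends on a rate that the documents do not give. One such subject can reverse a result at the boundary, and the nominal 5% level is passed once the assumed rate is a little above 2%, about one subject in 50. The plan should be corrected, because the remedy is small and removes the ambiguity before it can affect the test.

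**What to change.** - **Appendix A:** define failure of this component as no index endovascular procedure recorded as started for an enrolled subject, whatever the PFU answer and including a missing PFU form.
- **Section 5.1.1.2:** state that these subjects are failures and that the imaging-based exclusion does not apply to them.
- **No new time limit:** the change should not add a limit on the start of Phase 2 to the endpoint, since Section 2.3.1.2 contains none.

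The cost is one line in each place, using procedure data that are already collected. The downside for the sponsor is that the success rate may be slightly less favourable. If sites already have to update the PFU answer, the change only confirms existing practice.

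A separate matter, which does not affect how a non-starter is classified, is the Phase 1 Evaluation window. Table 2, footnote a, says: "Phase 1 Evaluation should be performed at least 24 hours after the revascularization procedure but within 30 days post treatment". The Protocol schedule allows up to 60 days after revascularization, and Table 4 allows up to 59 days before Phase 2. These statements must be reconciled.
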